13 STATISTICAL CONSIDERATIONS

13.1 Sample Size and Power Considerations

13.1.1 Phase 2

In the phase 2 period of the trial, a total of 396 participants will be recruited, 66 participants per intervention arm and 132 to the control group. This provides 90% power to detect an absolute difference of 17% (50% intervention, 33% control, odds ratio >2) in the proportion achieving improvement in discomfort from diarrhoea on the GSRS-IBS at 8 weeks, [26] with a 1-sided 20% significance level, assuming 10% of participants are lost to follow-up.

An absolute difference of 17% equates to a number needed to treat of 6. The IBS literature demonstrates consistently that therapies with a number needed to treat around this level are usually taken up in clinical practice, whereas there is often less enthusiasm for those with more modest effectiveness and a higher number needed to treat. This is a similar minimum clinically important difference to that we have stipulated in a trial in IBS, the EME-funded TRITON trial of ondansetron (15/74/01).

It is recommended that in a trial comparing one control group to several intervention arms, allocation should be in the ratio 1 to each intervention arm and the square root of the number of intervention arms to the control group, in order to maximise efficiency (smallest sample size for a given power). [35] In this case the ratio is 1:1:1:1:2.

13.1.2 Phase 3

If two interventions are carried forward from phase 2, a total of 491 participants are required: an additional 38 participants per intervention arm, and a further 19 participants in the control group (ratio 2:2:1). This will provide 90% power to detect a 16-point difference in the IBD-Q at 6 months, with 2-sided 2.5% significance, assuming an extra 10% of participants are lost to follow-up, and a standard deviation (SD) of 32. [36, 37] The final allocation ratio is 5:5:7 across both phases.

If only one intervention is carried forward from phase 2, a total of 426 participants are required: an extra 20 participants recruited to that intervention arm, and an extra 10 participants recruited to the control group (ratio 2:1). Again, this gives 90% power to detect a 16-point difference in the IBD-Q at 6 months, with 2-sided 5% significance, assuming an extra 10% lost to follow-up, and a SD of 32. [36, 37] The final allocation ratio is 5:8 across both phases.

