13.3.7 Primary Endpoint Analysis

The primary analysis in the phase 3 period will compare IBD-Q scores at 6 months between the control group and the intervention arms individually, in linear regression models adjusted for the stratification variables and baseline IBD-Q. Results will be expressed as point estimates, together with 95% or 97.5% confidence intervals (when there are one or two intervention arms, respectively), and p-values.

For the primary endpoints only, missing data will be multiply imputed, where appropriate. When questionnaires have missing items, scoring instructions specific to the questionnaires will be followed, or if no such instructions exist the summary scores will be calculated from the non-missing items, as long as at least half are non-missing.

Sensitivity analyses on a per-protocol population will test the robustness of the results.

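### With two arms in phase 3, a Holm step-down test would find a second effective arm more often than the planned fixed 2.5% tests, at the same 5% family-wise level; the planned tests are valid

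*Protocol*

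**What the plan says.** Section 13.1.2 of the protocol sizes the two-arm case "with 2-sided 2.5% significance, assuming an extra 10% of participants are lost to follow-up, and a standard deviation (SD) of 32". The target is 90% power for a 16-point IBD-Q difference at 6 months. If only one arm goes forward, the level is two-sided 5%: "with 2-sided 5% significance, assuming an extra 10% lost to follow-up, and a SD of 32".

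Section 13.3.7 compares each remaining arm with control separately, in a linear regression adjusted for the stratification variables and baseline IBD-Q. It gives results "together with 95% or 97.5% confidence intervals (when there are one or two intervention arms, respectively), and p-values".

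The level is thus 5% for one comparison and 2.5% for each of two, with matching interval widths. This is an equal Bonferroni split, although the protocol does not use the word. It mentions no step-down or other multiple-comparison procedure.

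**The concern.** An equal split holds each comparison to 2.5% whatever the other one shows. Once one arm has passed at 2.5%, control of the family-wise error at 5% no longer requires the other to meet 2.5%; it may be tested at 5%. Under the fixed split, a second arm with a p-value between 0.025 and 0.05 misses the threshold, although the 5% family-wise level would allow it to be declared effective.

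At stake is the second effective treatment in a trial designed to take up to two treatments forward. No extra participants are needed to recover the lost power.

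**Working it through.** **Inputs from section 13.1.** Phase 2 recruits "66 participants per intervention arm and 132 to the control group". The two-arm phase 3 adds "an additional 38 participants per intervention arm, and a further 19 participants in the control group (ratio 2:2:1").
- Randomised per active arm: 66 + 38 = 104. Control: 132 + 19 = 151.
- Effect 16 points; SD 32.
- Loss: 10% in phase 2 and an extra 10% in phase 3. I read this as 1 - 0.9 x 0.9 = 19%, or simply 20%. This reading is an assumption.

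**Reproducing the stated 90%.** At 20% loss the evaluable numbers are 83.2 per arm and 120.8 controls.
- SE = 32 x sqrt(1/83.2 + 1/120.8) = 4.56, so the expected z is 16/4.56 = 3.51.
- The two-sided 2.5% critical value is 2.241. Power = Phi(3.51 - 2.241) = 89.8%. At 19% loss it is 90.1%.
- In reverse, 90% power needs 122 evaluable controls and 84 per arm. Dividing by 0.81 gives 150.6 and 103.7, against the planned 151 and 104.

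The protocol's figure therefore reproduces.

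**Why Holm keeps the 5% level.** Holm tests the smaller p-value at 2.5% and, only if that is significant, the other at 5%.
- Both nulls true: an error needs at least one p-value at or below 2.5%, with probability at most 2 x 2.5% = 5%.
- One null true: an error needs that arm's p-value at or below 5%, with probability at most 5%.

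This holds for any correlation between the tests. Every Bonferroni rejection is also a Holm rejection.

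**Power.** The shared control gives the two test statistics a correlation of (1/151)/(1/104 + 1/151) = 104/255 = 0.408. Bivariate-normal simulation with 4 million draws gives the following, with 20% loss unless stated:

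| True effects | Quantity | Fixed 2.5% | Holm |
|---|---|---|---|
| 16 and 16 | each arm | 89.8% | 93.0% |
| 16 and 16 | both arms | 82.3% | 88.8% |
| 16 and 16 | at least one arm | 97.2% | 97.2% |
| 16 and 16, 10% loss | each arm | 93.1% | 95.6% |
| 16 and 16, 10% loss | both arms | 87.7% | 92.7% |
| 16 and 8 | stronger arm | 89.8% | 90.3% |
| 16 and 8 | weaker arm | 31.3% | 41.2% |
| 16 and 0 | effective arm | 89.8% | 89.9% |
| 0 and 0 | any false positive | 4.75% | 4.75% |

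At 19% loss with both effects 16, the figures are about 90% to 93% per arm and 82.9% to 89.3% for both.

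**Error in the mixed case.** With effects 16 and 0, the ineffective arm's Holm rejection rate is P(at least one) + P(both) - P(effective arm) = 90.3% + 4.2% - 89.9% = 4.6%, against 2.5% under the fixed split. It stays within 5%.

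**Baseline adjustment.** Section 13.3.7 adjusts for baseline IBD-Q, but the SD of 32 makes no allowance for this. With an assumed baseline correlation of 0.5 (not in the protocol), the residual SD is 32 x sqrt(1 - 0.25) = 27.7. At 20% loss and both effects 16, the gain falls to about 1.5 points per arm and 2.9 for both.

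**The case against.** The strongest reply is that nothing here is wrong. The split controls error, the sample size meets its 90% target at that level, and the intervals agree with the tests. All of that stands. A reader might infer that the trial is underpowered or its primary test defective; the reproduced 90% shows otherwise.

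A reader might also infer a general loss of 3 to 6 points of power. The documents do not support that. The figure needs both arms to have the full 16-point effect, and section 13.3.6 carries arms forward on an 8-week symptom response at p < 0.2, which does not establish a 6-month IBD-Q effect in each. With effects of 16 and 8 the stronger arm gains only 0.5 points. That figure alone understates the benefit, however, since the weaker arm gains about 10.

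It can be said that 13.3.7 sets interval widths and promises p-values, and never calls an arm negative, so a step-down rule could be left to the SAP. This carries limited weight. The 2.5% significance level is written into 13.1.2, the matching 97.5% intervals into 13.3.7, and no other decision rule is given.

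The objection about intervals has substance. Under Holm, a second arm with p between 0.025 and 0.05 is declared effective while its 97.5% interval includes zero. Agreement between test and interval is a legitimate reason to prefer the simple split, and giving it up requires an explicit reporting rule.

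**Conclusion.** The point holds as an optional, low-cost improvement. At the design assumptions, with both arms truly at 16 points, SD 32, total loss of 19-20% and no allowance for baseline adjustment, Holm adds about 3 points of power per arm and about 6 points to the chance of finding both. The gain is smaller if retention is better or baseline IBD-Q is predictive. It is about 0.15 points for an effective arm paired with an ineffective one, and nil for the chance of at least one success.

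The 5% level discussed here covers the two final comparisons only. It should not be read as covering the choice of up to two arms out of four in phase 2, which neither procedure addresses.

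**What to change.** Add to section 13.3.7: when two arms are carried forward, the two comparisons with control are tested by the Holm procedure, the smaller p-value at two-sided 2.5% and, if that is significant, the other at two-sided 5%. State also that the Holm decision governs significance, and that an arm declared effective at the second step may have a 97.5% interval that includes zero.

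Keep section 13.1.2 as the conservative planning level and keep the 97.5% intervals. The one-arm case is unaffected.

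The cost is two sentences, settled before any phase 3 outcome comparison is seen, and a footnote in the results if test and interval disagree. The sample size, regression model and data collection do not change.

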13.3.8 Secondary Endpoint Analysis

Secondary continuous endpoints (IBD-Q at 8 weeks, GSRS-IBS,HADS anxiety and depression scores, CRP, FC and constipation) will be analysed in the same manner as the primary endpoint, with the endpoint in question at baseline replacing the IBD-Q at baseline in the model. Secondary binary endpoints will be analysed similarly in logistic regression models. Other secondary endpoints pertaining to disease activity and tolerability (Escalation of Medical Therapy, Need for Surgery, and flares of disease activity)

An exploratory moderator analyses will be conducted to investigate if treatment effect varies by diarrhoea severity, disease extent, or mood at baseline, by testing the interaction between such effects and the treatment allocation. Similarly, the number of contacts or mood during follow-up will be tested to see if this mediates patient outcomes.

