13.2.3 Secondary Outcome Measures (at 8 Weeks and 6 Months Post-randomisation)

13.2.3.1 Loose Stools, Diarrhoea, Urgency, and Abdominal Pain

The GSRS-IBS, [26] which is described above, will be used to assess the effect of the various interventions on discomfort from loose stools, urgency, discomfort from diarrhoea and abdominal pain at both 8 weeks and 6 months.

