13.3.5 Descriptive Statistics

Descriptive statistics will be presented for demographics and baseline data, endpoints, and safety data. Continuous variables will be summarised by mean, SD, median, minimum, and maximum, as well as interquartile range, if appropriate. Categorical variables will be summarised by frequencies and percentages. A CONSORT diagram will display the flow of participants through the trial. Baseline characteristics of those lost to follow-up will be compared with those not lost to follow-up to assess for bias, and to inform the methods for handling missing data in inferential analyses.

13.3.6 Phase 2 Analysis and Progression to Phase 3

At the end of the phase 2 period, the diarrhoea responder rates at 8 weeks will be compared between the control group and each of the intervention arms individually, in logistic regression models adjusted for the stratification factors. Results will be expressed as odds ratios, together with 80% confidence intervals and p-values. Intervention arms will only be carried forward to phase 3 if the p-value in comparison with the control group is <0.2. This will correspond to an odds ratio >2, or to an absolute difference in response rate of 17%, when compared with the control group, if the response rate in the control group is 33%. If more than two intervention arms achieve this difference, the observed response rates, as well as safety, will be taken into account to decide which treatment arms should progress.

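### The 8-week diarrhoea result is used to choose the phase 3 arms, then estimated and tested again in those arms at the primary's nominal level; the retained-arm estimate is biased upward, and its intervals under-cover when the true effect is nil or small

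*Protocol*

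**What the plan says.** **Selection.** In Protocol 13.3.6, "the diarrhoea responder rates at 8 weeks will be compared between the control group and each of the intervention arms individually", and "Intervention arms will only be carried forward to phase 3 if the p-value in comparison with the control group is <0.2". If more than two arms pass, "the observed response rates, as well as safety, will be taken into account to decide which treatment arms should progress". Results are reported "together with 80% confidence intervals and p-values". The sample size in 13.1.1 is set "with a 1-sided 20% significance level, assuming 10% of participants are lost to follow-up".

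**Reuse.** Section 13.2.3.1 lists among the secondary outcomes "discomfort from diarrhoea and abdominal pain at both 8 weeks and 6 months". Section 3.3 and the trial summary also place it at both times. Section 13.3.8 fixes the method: "Secondary continuous endpoints (IBD-Q at 8 weeks, GSRS-IBS,HADS anxiety and depression scores, CRP, FC and constipation) will be analysed in the same manner". The model for that manner is the phase 3 primary analysis, which 13.3.7 gives as adjusted linear regression with 95% intervals (one arm) or 97.5% intervals (two arms) and p-values. Binary secondary endpoints get the logistic equivalent.

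**Data.** Section 13.3.2 runs the final analysis on the arms that remain. Section 13.1.2 counts phase 2 participants in the totals of 491 and 426: "The final allocation ratio is 5:5:7 across both phases". Section 13.3.3 analyses everyone randomised. Nothing in 13.3.8 treats 8-week diarrhoea differently from an outcome that played no part in selection.

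**The concern.** One measure at one time point first decides which arms survive and is then estimated and tested in the survivors, mostly on the same people. Arms whose phase 2 result was favourable by chance are over-represented among those kept. The phase 3 participants dilute that chance component but do not remove it. Relief of diarrhoea is the aim of the trial, and this measure is the phase 2 primary. A final-report estimate with a nominal interval and p-value would be read as confirming phase 2, when it largely repeats it.

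**Working it through.** **1. The plan's own figure.** With 66 v 132 and 10% loss, 59.4 v 118.8 are evaluable. For 50% v 33%, SE = √(0.25/59.4 + 0.2211/118.8) = 0.078 and 0.17/0.078 = 2.18. At one-sided 0.20, power = Φ(2.18 − 0.84) = 0.91, which matches the stated 90%. At two-sided 0.20, Φ(2.18 − 1.28) = 0.82. The design is therefore one-sided. However, 13.3.6 writes p<0.2 beside 80% intervals, which suits a two-sided reading, so both were run.

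**2. Overlap.** Two arms: 66/(66+38) = 66/104 = 63% of each retained arm and 132/151 = 87% of control. One arm: 66/86 = 77% and 132/142 = 93%.

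**3. Hand check, one null arm, one-sided gate.**
- Mean z given passing: φ(0.84)/0.20 = 0.280/0.20 = 1.40.
- SE of the phase 2 score difference in SD units: √(1/59 + 1/119) = 0.159.
- Correlation between a score and its dichotomy at 33%: φ(0.44)/√(0.33×0.67) = 0.362/0.470 = 0.77.
- Phase 2 bias: 1.40 × 0.159 × 0.77 = 0.172 SD.
- Pooling. The arm carries (1/59)/(1/59 + 1/119) = 0.67 of the variance and control 0.33. Adding 34 v 17 leaves 0.67×59/93 + 0.33×119/136 = 0.71 of the bias, or 0.12 SD. Adding 18 v 9 leaves 0.67×59/77 + 0.33×119/128 = 0.82, or 0.14 SD.
- Response scale: 1.40 × 0.470 × 0.159 = 10.5 points, diluted to 7.5 (two arms) or 8.6 (one arm).

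**4. Simulation of the whole design.** Four arms, 59 v 119 evaluable at phase 2. Responder means a latent score (higher is better) beyond the cut that gives 33% in control. Arms passing the gate are kept, at most the two with the highest observed rates. Then 34 v 17 or 18 v 9 are added, and the pooled mean difference is tested two-sided at 2.5% or 5%. There were 40,000 trials per scenario. Pairs are one-sided / two-sided gate.

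| True response, all active arms | True effect (SD) | Bias (SD) | Coverage |
|---|---|---|---|
| 33% (null) | 0 | 0.13 / 0.17 | 92% / 87% |
| 40% | 0.19 | 0.08 / 0.10 | 97% / 96% |
| 50% (design) | 0.44 | 0.05 / 0.05 | 97.5% / 97.6% |

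The true effects are normal-quantile differences: 0.44 − 0.25 = 0.19 at 40%, and 0.44 − 0 at 50%.

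With all arms null, 48% / 29% of trials reach phase 3. Of those, 10% / 16% declare a false 8-week benefit. Across all trials that is about 5%, against 2.5% in the benefit direction for a two-sided 5% family.

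**5. Response scale, separate simulation (log odds ratio intervals).** With all arms null, the mean risk difference is +8.1 / +10.2 points and coverage 91.8% / 82.8%, against a nominal mix of about 96%. With all arms truly +5, the estimate is +10.5 / +12.2. With all arms truly +17, it is +19.9 / +20.2 with coverage 97.8% on either gate. A null arm kept beside one truly effective arm shows +7.8 / +9.6.

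**6. Phase 3-only estimate.** The mean is within about 0.001 of the truth in every scenario, with coverage 97.8% to 98.6%. Precision is poor: SE = √(1/34 + 1/17) = 0.30 SD with two arms and √(1/18 + 1/9) = 0.41 SD with one.

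**7. IBD-Q primary.** With the latent correlation to 8-week diarrhoea varied from 0 to 0.9, the two-sided family-wise rate was 0.013 to 0.048.

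**The case against.** **A detail left to the SAP.** Section 13.3.8 gives no time point for GSRS-IBS and does not mention pooling, and labelling a secondary estimate is ordinary SAP content. It is true that the reading has to be assembled. But 13.2.3.1 supplies the time point, 13.1.2 and 13.3.3 supply the pooling, and 13.3.8 with 13.3.7 supplies the method. That is a stated rule which gives a biased result, and an SAP that follows it inherits the bias.

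**The size is overstated.** Three stronger readings are tempting, and the documents and figures do not support them.
- A reader might infer that the intervals under-cover in general. They do not. Coverage is near nominal at the design effect and only slightly low at +5 points on the one-sided gate (96.3% v 97.0%).
- A reader might infer that an ineffective arm which slipped through will probably look effective again. It usually will not: the figure is 10% to 16% of all-null trials that reach phase 3.
- A reader might infer that the trial's main conclusion is compromised. The IBD-Q test keeps its error rate, and the phase 2 gate itself is unchanged.

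The larger figures also belong to the two-sided reading of p<0.2, which does not reproduce the stated power.

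**The remedy is limited.** An exact conditional estimator cannot be built on the written rule, because the choice among more than two passing arms includes a discretionary safety judgement. Other outcomes correlated with 8-week diarrhoea also inherit part of the bias. At an assumed correlation of 0.6 that is about 0.6 × 0.13 to 0.17 = 0.08 to 0.10 SD under the null. Both points stand. They narrow the fix to the endpoint actually used for selection and do not remove the case for it.

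**Conclusion.** The concern holds for one secondary endpoint. In retained arms the pooled 8-week diarrhoea estimate is biased upward in every scenario examined. On the stated one-sided gate the bias is about 0.13 SD (roughly 8 response points) for null arms, 0.08 SD if all arms respond at 40%, and 0.05 SD on a true 0.44 SD (about 11%) at the design effect. The two-sided reading gives 0.17, 0.10 and 0.05 SD. Under-coverage is confined to nil or small effects, about 92% or 87% under the null against nominal 95% to 97.5%. The excess error is mainly conditional on an arm having been kept. Over the whole design the benefit-direction error is about 5% against 2.5%.

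These figures assume 33% control response, 10% loss, a normal latent score, no covariate adjustment, and safety playing no part in the choice of arms. This should be corrected, but it does not threaten the primary analysis.

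**What to change.** In 13.3.8, exempt 8-week GSRS-IBS diarrhoea (score and responder) from the rule that secondary endpoints follow the primary analysis, and state instead:

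1. The phase 2 comparison of all four arms, already in 13.3.6, is the inferential analysis of this endpoint.
2. The pooled estimate for retained arms is descriptive, carries no nominal p-value, and is reported with a statement that it is not independent of arm selection.
3. The estimate from participants randomised in phase 3 only is shown beside it, described as unbiased but imprecise.
4. Optionally, a selection-adjusted estimate conditioning on the p<0.2 gate is added as a sensitivity analysis, with the caveat that the safety part of the choice cannot be modelled. This requires 13.3.6 to say whether p<0.2 is one-sided or two-sided.

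The 6-month diarrhoea analysis and the IBD-Q primary can stay as written. The cost is a wording change, a small extra analysis of data already collected, and the loss of one nominal secondary p-value.

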At week 16, halfway through this reintroduction phase, all responders will receive a telephone call to discuss the FODMAP reintroduction and to encourage study retention and dietary

adherence. Dietitians will support participants with FODMAP personalisation (increasing dietary and nutritional variety whilst maintaining symptom control) if participants have completed the reintroduction process.

Dietitian and/or Nurse Appointment 3

After 24 weeks, each participant will return for a final 30-minute face-to-face session at the site's usual outpatient dietetic clinic room setting to reassess dietary adherence. For all responders, this will be with a dietitian and research nurse. For non-responders to the low FODMAP diet, this will be with the research nurse only for final data collection.

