9.2.2 Treatment Arm Specific Assessments – Overview

For full details of the treatment specific assessments please see section 8 and the Schedule of Events. In summary:

Control Group: no additional assessments

Low FODMAP Arm:

- Face-to-Face appointments with the dietitian during week 1 and after week 8 for participants randomised to this arm.
- Telephone call (16 weeks) and face-to-face appointment (24 weeks) with dietitian for responders only. All participants (including non-responders) will also see a research nurse at 24 weeks as per section 9.2.2 below.

Drug Intervention Arms:

- Telephone calls from the research nurse at weeks 1 and 3, and month 3, postrandomisation. Please refer to the treatment specific guidance provided for each individual study drug in section 8 for details.
- Participant diary cards participants to record the number the number of tablets they have taken each day on diary cards from start to completion of study treatment. The diary cards are to be used as participant guidance so participants can monitor their own adherence to medication.

Assessments to be carried out for all patients in all arms are detailed below in section 9.2.3.

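### Number of contacts is planned as a mediator, but contacts are set by arm and, in the diet arm after week 8, by response, so a 6-month result cannot be read as mediation

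*Protocol*

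**What the plan says.** Section 13.3.8 first describes moderator tests: "An exploratory moderator analyses will be conducted to investigate if treatment effect varies by diarrhoea severity, disease extent, or mood at baseline". It then adds that "the number of contacts or mood during follow-up will be tested to see if this mediates patient outcomes". It does not define a contact, give a time window or name a model for the mediator test.

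The contact schedule is in section 9.2.2, with detail in section 8:

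- Control: "Control Group: no additional assessments".
- Each drug arm: "Telephone calls from the research nurse at weeks 1 and 3, and month 3, postrandomisation".
- Diet arm, everyone: "Face-to-Face appointments with the dietitian during week 1 and after week 8 for participants randomised to this arm".
- Diet arm, after week 8: "Telephone call (16 weeks) and face-to-face appointment (24 weeks) with dietitian for responders only". Section 8.1.4 agrees: "At week 16, halfway through this reintroduction phase, all responders will receive a telephone call". Of the final session it says: "For non-responders to the low FODMAP diet, this will be with the research nurse only for final data collection".

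Section 8.1.4 makes responder status the dietitian's judgement at the second appointment, based on adherence and on whether overall gut symptoms have improved.

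Two other sources of variation exist. Sections 8.2.4, 8.3.4 and 8.4.4 offer drug-arm participants a gastroenterologist review at about one month if they or the nurse have queries or concerns. Section 9.2.2.1.1 provides reminder calls for participants completing paper questionnaires.

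**The concern.** A mediator should be something that treatment changes and that then changes the outcome. In the diet arm after week 8 the order is reversed: the participant improves, and the extra dietitian contacts follow because of it. People who are better at week 8 are likely to be better at 6 months with or without those contacts, so an analysis of 6-month outcomes would tend to credit the contacts with a benefit that came before them.

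In the drug arms every participant has the same three scheduled calls, so scheduled contact carries the same information as allocation. What varies is mostly an optional review prompted by concerns, which may mark people who are doing worse.

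The analysis could therefore suggest that more dietitian time improves quality of life, or that nurse and clinician contact harms it, when neither is true. A choice of model in an analysis plan would not remove this, because the problem lies in how the contacts arise.

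**Working it through.** **1. The plan's own figure, used to fix the sample size for the check.** The mediator sentence states no number, so I took the phase 3 size from section 13.1.2. With two arms carried forward, the arm has 66 + 38 = 104 participants and control has 132 + 19 = 151. The target is 16 IBD-Q points, SD 32, two-sided 2.5%, 90% power. Power = Φ(16 / [32·√(1/n₁ + 1/n₂)] − 2.241).

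- 10% loss (93.6 vs 135.9): SE = 4.30, 16/4.30 = 3.72, power 93.1%.
- 20% loss (83.2 vs 120.8): SE = 4.56, 16/4.56 = 3.51, power 89.8%.

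The stated 90% is reproduced at 20% total loss, reading the extra 10% as cumulative. The check uses 83 vs 121.

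**2. Drug arm vs control, scheduled contacts only.** Contacts are 3 in the drug arm and 0 in control, so contacts = 3 × arm. The matrix [1, arm, contacts] has rank 2 of 3, and no contact effect separate from arm can be estimated from scheduled contacts.

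**3. Diet arm vs control.** Dietitian contacts are 0 in control, 2 for diet non-responders and 4 for diet responders. With arm in the model and no variation in control, the contact coefficient is

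(responder mean − non-responder mean, within the diet arm) / 2.

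A 16-point responder gap gives 16/2 = 8 points per contact even when contacts do nothing. Counting one extra contact instead of two rescales the coefficient but leaves the test unchanged.

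**4. False-positive rate, diet arm.** The protocol does not give the link between week-8 responder status and 6-month IBD-Q, so it is assumed over a range. A latent week-8 variable L and the 6-month IBD-Q have correlation r; the top 33% on L are responders (section 13.1.1's control rate on the GSRS-IBS, borrowed as an assumption). There is no treatment or contact effect. The model is a linear regression on arm and contacts, tested at 5%, with 83 vs 121.

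| r | Unadjusted | Adjusted for baseline IBD-Q |
|---|---|---|
| 0.2 | about 28% | about 5% to 13% |
| 0.3 | about 55% to 57% | about 18% to 36% |
| 0.5 | about 96% | about 82% to 92% |

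The adjusted column spans two assumed settings: baseline correlated 0.6 with outcome and 0.3 with L (lower figures), or 0.5 and 0.2 (upper figures). The reduction follows from the partial association, r minus the product of the two baseline correlations. At r = 0.2 it is 0.2 − 0.18 = 0.02 in the first setting and 0.2 − 0.10 = 0.10 in the second. At r = 0.5 it is 0.32 and 0.40.

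**5. Cross-check on the IBD-Q scale.** A separate unadjusted simulation used 104 vs 151 with 80% retained, response of 50% vs 33%, and no contact effect. It rejects in 5%, 23%, 61%, 94% and over 99% of trials for responder gaps of 0, 8, 16, 24 and 32 points. At 16 points the mean estimate is about +8 per contact, as step 3 predicts. With 33% response in both arms the rate is 57%; with phase 2 numbers (66 vs 132, 90% retained) it is 48%.

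**6. Drug arms with the optional review counted.** If 10% to 30% take the review (assumed), the coefficient becomes estimable. It holds 5% when reviews are unrelated to outcome. If those with concerns score 16 points lower (assumed), it rejects in 28% to 56% of trials, with a negative sign.

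**The case against.** The case on the other side has several parts, and most of them limit the point.

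- **No model is stated.** A reader might infer from section 13.3.8's linking word that mediators will be tested by an interaction with allocation, and conclude that the test cannot be estimated at all. The interaction belongs to the moderator sentence; the mediator sentence specifies no model. Definitions and methods for an exploratory analysis can be left to an analysis plan. This stands against any claim of strict non-estimability.
- **Contacts do vary within arms.** The optional reviews and reminder calls mean the drug-arm coefficient need not be inestimable. This stands too, but reviews follow concerns and reminders follow questionnaire mode and late return, so neither supplies variation that supports a causal reading.
- **The size depends on assumptions.** Section 13.3.8 analyses secondary endpoints in the same manner as the primary, which adjusts for baseline. Under one assumed setting that removes the excess at the low end. Diet responder status also includes adherence, and the protocol gives neither its rate nor its correlation with IBD-Q. This stands, and the range above reflects it.
- **Unequal contact is a fair question in an open-label trial.** It is, but post-week-8 contacts granted because of response cannot answer it.

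**Conclusion.** The planned test is wrong as written, at low severity. For 6-month outcomes, contact count in the diet arm is partly a consequence of week-8 response, and in the drug arms scheduled contact cannot be separated from allocation. An association with outcome therefore cannot be read as mediation.

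With no true contact effect, the nominal 5% test in the diet arm rejects in about 28% to 96% of trials unadjusted and about 5% to 92% with baseline adjustment. This rests on assumed correlations of 0.2 to 0.5 between week-8 response and 6-month IBD-Q, the two assumed baseline settings, 33% responders and 83 vs 121 evaluable. The diet would also have to be one of two arms carried forward.

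A reader might infer that the test must either fail to run or reject. The protocol does not support that: some within-arm variation exists, and rejection stays near 5% if responders do no better at 6 months in an unadjusted model. Nor does the problem reach 8-week outcomes, because the responder-only contacts come later. The primary analyses, the choice of arms for phase 3 and the mood mediator are untouched.

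**What to change.** In section 13.3.8, remove the number of contacts from the mediation sentence and leave mood. Report contacts descriptively by arm, and state that scheduled contact is confounded with arm by design.

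If any contact analysis is kept, exclude diet-arm contacts that depend on week-8 response, define which contacts count, and label the result as non-causal.

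The cost is one sentence and the loss of one exploratory analysis. No data collection, sample size or primary analysis changes.
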